10.4.3	SAE/Unanticipated Adverse Device Effect (UADE)/Unanticipated Serious Adverse Device Effect (USADE) Reporting	41
10.4.4	Device Deficiency (DD) Reporting	41
10.5	PREGNANCY	41
10.6	POTENTIAL ADVERSE EVENTS	42
10.7	POTENTIAL BENEFITS.....	43
11	STUDY MONITORING	43
12	ETHICAL AND REGULATORY CONSIDERATIONS	44
12.1	SUBJECT INFORMATION AND CONSENT	44
12.2	DECLARATION OF HELSINKI	44
12.3	ISO 14155:2011 CLINICAL INVESTIGATION OF MEDICAL DEVICES FOR HUMAN SUBJECTS- GOOD CLINICAL PRACTICE.....	44
12.4	ADDITIONAL REGULATORY CONSIDERATIONS	44
12.5	STUDY INITIATION/CONDUCT.....	44
12.6	COMPLIANCE WITH THE CLINICAL STUDY PROTOCOL.....	44
12.7	PROTOCOL DEVIATIONS (PDs)	45
12.8	PROTOCOL AMENDMENTS.....	45
12.9	PUBLICATION POLICY	45
12.10	INSURANCE AND INDEMNITY	45
13	REFERENCES.....	46

RXSIGHT, INC.**PROTOCOL NO. CSP-036-MX****A SINGLE CENTER EXPLORATORY STUDY TO EVALUATE THE USE OF THE
RXSIGHT LIGHT ADJUSTABLE LENS (LAL) AND THE LIGHT DELIVERY
DEVICE (LDD) TO IMPROVE VISUAL OUTCOMES****1 STUDY SYNOPSIS****STUDY OBJECTIVE**

The objective of this study is to evaluate, for the visual correction of aphakia, whether the RxSight Light Adjustable Lens (LAL) and Light Delivery Device (LDD) can be used to improve visual outcomes after performing adjustments of the LAL with the LDD. This is an exploratory study. No primary effectiveness endpoints will be defined.

STUDY POPULATION

The study population will consist of up to 200 eyes in up to 100 subjects implanted with the LAL. A subset of the population may include study subjects who were already implanted with the LAL under RxSight's CSP-037-MX protocol "A Single Center Exploratory Study to Evaluate the Effects of Ambient Sunlight Exposure on the RxSight Light Adjustable Lens (LAL)" but who have not received light treatments with the LDD. Subject's eyes must meet all applicable inclusion criteria and none of the exclusion criteria as described.

STUDY DESIGN

A prospective, single center, exploratory study will be conducted. Subjects will be followed until completion of the Postop Month 6 or later follow-up visit.

Patients who require cataract extraction and intraocular lens implantation will be pre-screened for eligibility as part of pre-entry activity. If one or both eyes meet inclusion/exclusion criteria, delegated and trained study staff will explain the study purpose, procedures, risks/benefits and subject responsibilities to the potential participant. Written informed consent must be obtained prior to initiation of any clinical procedures that are performed solely for the purpose of determining eligibility for research. The patient is enrolled upon signing the informed consent. Both eyes of all subjects may be screened for eligibility at the same preoperative visit. If at any time during the preoperative visit, an eye does not meet inclusion or exclusion criteria, screening for that eye can be discontinued immediately. If only one eye is being screened, then the subject will be exited from the study. If both eyes of the subject are enrolled for study participation, each eye will be scheduled for surgery within a timeframe of the investigator's choice but on separate days.

Patients from RxSight's CSP-037-MX study may have both eyes screened for study eligibility. The former CSP-037-MX study eye must meet all inclusion/exclusion criteria as specified below for subjects who previously participated in CSP-037-MX. If applicable, the

fellow eye (non-CSP-037-MX study eye) must meet all inclusion/exclusion criteria as specified below for subjects who did not previously participate in CSP-037-MX. If only the prior CSP-037-MX study eye is being considered for this study, the subject will need to review and sign only a CSP-036-MX written informed consent for former CSP-037-MX subjects. If both eyes are being considered for this study, the subject will also have to review and sign a CSP-036-MX written informed consent for subjects who had no affiliation with CSP-037-MX.

At the discretion of the Principal Investigator, a subgroup of eyes will receive an [REDACTED] [REDACTED] 7-14 days postop. Commencing 17 to 30 days postop, all eyes will receive up to three adjustments and one to two lock-in treatments. Each light treatment will be separated by 2 to 7 days. The type of adjustment (spherocylindrical and/or presbyopia) the study eye receives is dependent on specific criteria at each light adjustment visit. Postoperatively, all subjects will undergo ophthalmic examinations until completion of the Postop Month 6 or later follow-up visit.

For subjects that receive only non-presbyopic adjustments, uncorrected distance visual acuities will be presented and summarized. For subjects that receive a presbyopia adjustment, uncorrected distance, uncorrected intermediate and uncorrected near acuities will be presented and summarized. Additional analyses may be performed. Safety for all study eyes will be evaluated per ISO 11979-7.

DURATION OF STUDY

Each subject will participate in the study for approximately 6-12 months. The recruitment phase is expected to last approximately 10 months. The complete study period is expected to be approximately 24 months.

STUDY SITE

The study will be performed in an ophthalmology clinic. The investigator will be an ophthalmic surgeon, specializing in cataract surgery with implantation of intraocular lenses. Study responsibilities will be registered in a delegation log that will be kept at the investigational site. The overall responsibility at the study clinic remains with the investigator.

INCLUSION CRITERIA FOR SUBJECTS WHO DID NOT PREVIOUSLY PARTICIPATE IN CSP-037-MX

- Must sign a written Informed Consent form and be willing to undergo cataract surgery for the implantation of the LAL.
- Age 30 or older on the day cataract surgery is performed.
- Preoperative keratometric cylinder ≤ 3.50 D.
- Study eye must have a cataract causing reduction in best corrected distance visual acuity (BCDVA) to a level of 20/32 or worse with or without a glare source.
- In subjects with only one eye enrolled in the study: Potential for BCDVA of 20/40 or better in the non-study eye after cataract removal and IOL implantation.

- Study eye has BCDVA projected to be 20/20 or better after cataract removal and IOL implantation as estimated by potential acuity meter (PAM) or surgeon estimation.
- Study eye has clear intraocular media other than cataract.
- Willing and able to comply with the requirements for study specific procedures and visits.
- Study eye has average dilated pupil diameter of ≥ 7.0 mm.
- Study eye requires an IOL power within the range available for the LAL.

INCLUSION CRITERIA FOR SUBJECTS WHO PREVIOUSLY PARTICIPATED IN CSP-037-MX

- Subject was previously enrolled within clinical study CSP-037-MX sponsored by RxSight, Inc. and meets the following inclusion criteria:
 - Potential for BCDVA of 20/40 or better in the non-study eye
 - Willing and able to comply with the requirements for study specific procedures and visits.
 - Former CSP-037-MX study eye can adequately dilate (enough of the edge of the LAL optic can be visualized to allow for centration during LDD light treatment).

EXCLUSION CRITERIA FOR SUBJECTS WHO DID NOT PREVIOUSLY PARTICIPATE IN CSP-037-MX

- Study eye with zonular laxity or dehiscence.
- Study eye with pre-existing macular disease that in the opinion of the investigator performing LDD light treatments would not be in the best interest of the patient.
- Study eye with retinal degenerative disorder (other than macular degeneration) that is expected to cause future vision loss.
- Subjects with diabetes with any evidence of retinopathy.
- Study eye with a history of uveitis.
- Study eye with significant anterior segment pathology, such as rubeosis iridis, aniridia, or iris coloboma.
- Study eye with corneal pathology that is either progressive or sufficient to reduce BCDVA to worse than 20/20.
- Study eye with any corneal dystrophy including basement membrane dystrophy that in the opinion of the investigator may confound the outcome.
- Study eye with keratoconus or suspected of having keratoconus.
- Study eye that has undergone previous intraocular surgery.
- Study eye with previous trauma or developmental defects in which appropriate support of the intraocular lens (IOL) is not possible.
- Subjects with serious co-morbid conditions that in the judgment of the investigator makes inclusion in the study not in the best interest of the subject.

- Subjects taking systemic medication that may increase sensitivity to UV light such as tetracycline, doxycycline, psoralens, amiodarone, phenothiazines, chloroquine, hydrochlorothiazide, hypericin, ketoprofen, piroxicam, lomefloxacin, and methoxsalen. LDD treatment in patients taking such medications may lead to irreversible phototoxic damage to the eye. This is only a partial list of photosensitizing medications. Please evaluate all medications that the patient is taking for this effect prior to consideration for implantation.
- Subjects taking a systemic medication that is considered toxic to the retina such as tamoxifen.
- Subjects who the doctor believes will be unable to maintain steady fixation that is necessary for centration of the LDD light treatment in the study eye.
- Study eye with irregular astigmatism.
- Study eye with history of ocular herpes simplex virus.
- Current vitreoretinal disease or a high risk of future vitreoretinal disease that may require silicone oil as part of therapy in the study eye.

EXCLUSION CRITERIA FOR SUBJECTS WHO PREVIOUSLY PARTICIPATED IN CSP-037-MX

- Subjects taking systemic medication that may increase sensitivity to UV light such as tetracycline, doxycycline, psoralens, amiodarone, phenothiazines, chloroquine, hydrochlorothiazide, hypericin, ketoprofen, piroxicam, lomefloxacin, and methoxsalen. LDD treatment in patients taking such medications may lead to irreversible phototoxic damage to the eye. This is only a partial list of photosensitizing medications. Please evaluate all medications that the patient is taking for this effect prior to light treatments.
- Subjects taking a systemic medication that is considered toxic to the retina such as tamoxifen.
- Subjects who the doctor believes will be unable to maintain steady fixation that is necessary for centration of the LDD light treatment in the study eye.
- Former CSP-037-MX study eye with history of ocular herpes simplex virus.

Outcome Parameters

The following visual performance parameters will be collected and summarized for eyes that received only non-presbyopic adjustments.

- % of eyes with UCDVA of 20/20 or better at Postop Month 6 or later

The following visual performance parameters will be collected and summarized for eyes that received a presbyopia adjustment.

- Proportion of eyes simultaneously with (1) Monocular UCDVA of 20/25 or better and (2) Monocular UCIVA of 20/32 or better and (3) Monocular UCNVA of 20/40 or better at Postop Month 6 or later.

Additional analyses may be performed. Clinical data for eyes receiving only non-presbyopic adjustments and eyes receiving a presbyopia adjustment may be summarized and analyzed separately. In addition, clinical data for former CSP-037-MX study eyes may be analyzed separately.

Safety Parameters:

- Incidence of persistent sight-threatening complications and adverse events and cumulative events defined per ISO 11979-7.

The incidence of all other adverse events will also be presented.

Examination Schedule:

Evaluation	Subjects who did not previously participate in CSP-037-MX or Former CSP-037-MX subjects fellow eye (non-CSP-037-MX study eye) enrolled	Former CSP-037-MX subjects with only former CSP-037-MX study eye enrolled
Preoperative	Day -60 to Day -1	NA
Operative	Day 0, day of surgery	NA
Postop Day 1	Days 1 to 2 postop	NA
████████ ¹	Days 7-14 postop	NA
Postop Week 3	Days 17 to 30 days postop: Adjustment #1	Days 17 to 30 days postop: Adjustment #1
Adjustment #2, if needed	2 to 7 days post Adjustment #1	2 to 7 days post Adjustment #1
Adjustment #3, if needed	2 to 7 days post Adjustment #2	2 to 7 days post Adjustment #2
Lock-in #1	2 to 7 days post final adjustment	2 to 7 days post final adjustment
Lock-in #2, if needed	2 to 7 days post lock-in #1	2 to 7 days post lock-in #1
Post Lock-in	7 to 14 days post final lock-in	7 to 14 days post final lock-in
Postop Month 3	Days 90 to 150 postop	Days 90 to 150 postop
Postop Month 6 or later	Days 180 to 400 postop	Days 180 to 400 postop

¹ Subgroup of eyes determined by the principal investigator

Unscheduled visits falling outside the designated ranges for scheduled visits will be considered “interim” visits for data recording purposes and a report form will be completed.

Clinical Parameters:

4. Demographics
5. Ocular History
6. History of Medications
7. Subjective symptoms/complaints (subject reported)
8. Ocular Biometry: Axial length + Anterior Chamber Depth
9. Corneal Topography
10. Autorefraction
11. Undilated photopic pupil diameter
12. Corneal Keratometry
13. Vision Quality Measurement
14. Anterior Segment OCT
15. Posterior Segment SD-OCT
16. Monocular uncorrected distance visual acuity (UCDVA)
17. Binocular uncorrected distance visual acuity
18. Manifest Refraction
19. Monocular best corrected distance visual acuity (BCDVA)
20. Ocular Dominance Test
21. Depth of focus testing
22. Monocular distance corrected intermediate visual acuity (DCIVA)
23. Monocular distance corrected near visual acuity (DCNVA)
24. Monocular uncorrected near visual acuity (UCNVA)
25. Binocular uncorrected near visual acuity
26. Binocular uncorrected intermediate visual acuity
27. Monocular uncorrected intermediate visual acuity (UCIVA)
28. In-office Erythropsia assessment
29. City University Color Test
30. Monocular Distance corrected contrast sensitivity: Mesopic/Photopic with and w/o glare
31. Intraocular pressure
32. Slit lamp exam
33. Fundus Exam
34. Aberrometry
35. Dilated pupil diameter

36. Adverse Event

ABBREVIATIONS AND DEFINITION OF TERMS

ACD	Anterior Chamber Depth
ADE	Adverse Device Effect
AE	Adverse Event
ANSI	American National Standards Institute
BCDVA	Best Corrected Distance Visual Acuity
CCC	Continuous Circular Capsulorhexis
CDRH	Center for Devices and Radiological Health
CFR	Code of Federal Regulations
CRF	Case Report Form
CRO	Contract Research Organization
CSP	Clinical Study Protocol
D	Diopter
DCIVA	Distance Corrected Intermediate Visual Acuity
DCNVA	Distance Corrected Near Visual Acuity
DD	Device Deficiency
DOF	Depth of Focus
EC	Ethics Committee
ETDRS	Early Treatment Diabetic Retinopathy Study
FDA	Food and Drug Administration
GCP	Good Clinical Practice
ICH	International Conference on Harmonization
IDE	Investigational Device Exemption
IOL	Intraocular Lens
IOP	Intraocular Pressure
IRB	Institutional Review Board
ISO	International Organization for Standardization
LD ^D	Light Delivery Device
M	Month
MR	Manifest Refraction
MRCYL	Manifest Refraction Cylinder
MRSE	Manifest Refraction Spherical Equivalent
OD	Right eye
OS	Left eye
PCO	Posterior Capsular Opacity
PI	Principal Investigator
PPC	Precision Pulse Capsulotomy

LAL	RxSight Light Adjustable Lens
SAE	Serious Adverse Event
SD	Standard Deviation
SE	Spherical Equivalent
SSI	Secondary Surgical Intervention
UADE	Unanticipated Adverse Device Effect
UCDVA	Uncorrected Distance Visual Acuity
UCIVA	Uncorrected Intermediate Visual Acuity
UCNVA	Uncorrected Near Visual Acuity
UP	Unanticipated Problem
UV	Ultraviolet

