6 STUDY POPULATION

The study population will consist of up to 200 eyes in up to 100 subjects implanted with the LAL. A subset of the population may include study subjects who were already implanted with the LAL under RxSight's CSP-037-MX protocol "A Single Center Exploratory Study to Evaluate the Effects of Ambient Sunlight Exposure on the RxSight Light Adjustable Lens (LAL)" but who have not received light treatments with the LDD. Subject's eyes must meet all applicable inclusion criteria and none of the exclusion criteria as described.

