6.2 EXCLUSION CRITERIA FOR SUBJECTS WHO DID NOT PREVIOUSLY PARTICIPATE IN CSP-037-MX

- Study eye with zonular laxity or dehiscence.
- Study eye with pre-existing macular disease that in the opinion of the investigator performing LDD light treatments would not be in the best interest of the patient.
- Study eye with retinal degenerative disorder (other than macular degeneration) that is expected to cause future vision loss.
- Subjects with diabetes with any evidence of retinopathy.
- Study eye with a history of uveitis.
- Study eye with significant anterior segment pathology, such as rubeosis iridis, aniridia, or iris coloboma.
- Study eye with corneal pathology that is either progressive or sufficient to reduce BCDVA to worse than 20/20.
- Any corneal dystrophy including basement membrane dystrophy in either eye that in the opinion of the investigator may confound the outcome.
- Study eye with keratoconus or suspected of having keratoconus.

- Study eye that has undergone previous intraocular surgery.
- Study eye with previous trauma or developmental defects in which appropriate support of the intraocular lens (IOL) is not possible.
- Subjects with serious co-morbid conditions that in the judgment of the investigator makes inclusion in the study not in the best interest of the subject.
- Subjects taking systemic medication that may increase sensitivity to UV light such as tetracycline, doxycycline, psoralens, amiodarone, phenothiazines, chloroquine, hydrochlorothiazide, hypericin, ketoprofen, piroxicam, lomefloxacin, and methoxsalen. LDD treatment in patients taking such medications may lead to irreversible phototoxic damage to the eye. This is only a partial list of photosensitizing medications. Please evaluate all medications that the patient is taking for this effect prior to consideration for implantation.
- Subjects taking a systemic medication that is considered toxic to the retina such as tamoxifen.
- Subjects who the doctor believes will be unable to maintain steady fixation that is necessary for centration of the LDD light treatment in the study eye.
- Study eye with irregular astigmatism.
- Study eye with history of ocular herpes simplex virus.
- Current vitreoretinal disease or a high risk of future vitreoretinal disease that may require silicone oil as part of therapy in the study eye.

EXCLUSION CRITERIA FOR SUBJECTS WHO PREVIOUSLY PARTICIPATED IN CSP-037-MX

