- Subjects taking systemic medication that may increase sensitivity to UV light such as tetracycline, doxycycline, psoralens, amiodarone, phenothiazines, chloroquine, hydrochlorothiazide, hypericin, ketoprofen, piroxicam, lomefloxacin, and methoxsalen. LDD treatment in patients taking such medications may lead to irreversible phototoxic damage to the eye. This is only a partial list of photosensitizing medications. Please evaluate all medications that the patient is taking for this effect prior to light treatments.
- Subjects taking a systemic medication that is considered toxic to the retina such as tamoxifen.
- Subjects who the doctor believes will be unable to maintain steady fixation that is necessary for centration of the LDD light treatment in the study eye.

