7.4 EXAMINATION SCHEDULE

Evaluation	Subjects who did not previously participate in CSP-037-MX or Former CSP-037-MX subjects with fellow eye (CSP-037-MX non-study eye) enrolled	Former CSP-037-MX subjects with only former CSP-037-MX study eye enrolled
Preoperative	Day -60 to Day -1	NA
Operative	Day 0, day of surgery	NA
Postop Day 1	Days 1 to 2 postop	NA
¹	Days 7-14 postop	NA
Postop Week 3	Days 17 to 30 days postop: Adjustment #1	Days 17 to 30 days postop: Adjustment #1
Adjustment #2, if needed	2 to 7 days post Adjustment #1	2 to 7 days post Adjustment #1
Adjustment #3, if needed	2 to 7 days post Adjustment #2	2 to 7 days post Adjustment #2
Lock-in #1	2 to 7 days post final adjustment	2 to 7 days post final adjustment
Lock-in #2, if needed	2 to 7 days post lock-in #1	2 to 7 days post lock-in #1
Post Lock-in	7 to 14 days post final lock-in	7 to 14 days post final lock-in
Postop Month 3	Days 90 to 150 postop	Days 90 to 150 postop
Postop Month 6 or later	Days 180 to 400 postop	Days 180 to 400 postop

¹ Subgroup of eyes determined by the principal investigator

Unscheduled visits falling outside the designated ranges for scheduled visits will be considered “interim” visits for data recording purposes. A report form will be completed for interim visits on the study eye.

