³ Tests indicated with an “X” must be performed at each unscheduled visit. Other tests may be conducted based on the investigator’s assessment of the subject.

⁴ Only required for subjects who previously participated in RxSight’s CSP-037-MX study

*Visits only required for subjects who did not previously participate in RxSight’s CSP-037-MX study

**Subgroup of eyes based on decision made by Principal Investigator

Visits	Preop*	Preop*	Operative*	Postop Day 1*	Postop Day 1*	Postop Week 3	Postop Week 3	Adjustment #2 (if needed)	Adjustment #3 (if needed)	Lock-in #1	Lock-in #2 (if needed)	Postop Month 3	Postop Month 3	Postop Month 6 or later	Unscheduled Visit ³
Visits	Preop*	Operative*	Operative*	Postop Day 1*	Postop Day 1*	Postop Week 3	Postop Week 3	Adjustment #2 (if needed)	Adjustment #3 (if needed)	Lock-in #1	Lock-in #2 (if needed)	Post Lock-in	Post Lock-in	Postop Month 6 or later	Unscheduled Visit ³
Anterior Segment OCT				X	X	X	X	X	X	X	X	X	X	X	
Posterior Segment SD-OCT					X ²	X ^{2, 5}					X ²				
Vision Quality Measurement				X	X	X	X	X	X	X	X	X	X	X	
Monocular Uncorrected Distance Visual Acuity (UCDVA)	X			X	X	X	X	X	X	X	X	X	X	X	X
Binocular Uncorrected Distance Visual Acuity					X ¹	X ^{1, 1, 2}					X ^{1, 2}	X ^{1, 2}	X ^{1, 2}		
Manifest Refraction	X				X	X	X	X	X	X	X	X	X	X	
Monocular Best Corrected Distance Visual Acuity (BCDVA)	X				X	X	X	X	X	X	X	X	X	X	
Ocular Dominance Test	X				X	X ⁵									
DOF Testing					X ²	X ^{2, 5}			X ²		X ²	X ²	X ²		
Monocular Distance Corrected Intermediate Visual Acuity					X ²	X ^{2, 5}			X ²		X ²	X ²	X ²		
Monocular Distance Corrected Near Visual Acuity					X ²	X ^{2, 5}			X ²		X ²	X ²	X ²		

¹ Only performed on subjects with both eyes enrolled and successfully implanted

^{1,1} Only performed on subjects with both eyes enrolled and successfully implanted and subject did not have an visit.

² May be performed on a subgroup of subjects as described in section 7.3.2.2 of the protocol

³ Tests indicated with an "X" must be performed at each unscheduled visit. Other tests may be conducted based on the investigator's assessment of the subject.

⁴ Only required for subjects who previously participated in RxSight's CSP-037-MX study.

⁵ Only performed on subjects who did not have an [REDACTED] visit.

*Visits only required for subjects who did not previously participate in RxSight's CSP-037-MX study.

** Subgroup of eyes based on decision made by Principal Investigator.

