The LAL must be implanted following specific surgical procedures. If these procedures are not followed by the surgeon, the lens may become scratched or improperly placed in the eye and may need to be explanted prior to light treatments. In order to perform the lens adjustment or the lens lock-in procedures, the subject's pupil needs to be adequately dilated. If this cannot be accomplished for any reason, additional eye drops, injections into the eye, or surgery may need to be utilized to adequately dilate the pupil. If the pupil cannot be adequately dilated after these types of treatments, the LAL may need to be explanted. An unpredicted change in vision can occur resulting from ocular exposure to daylight or any other UV source before the LAL is locked-in. The light treatments may not improve vision and/or manifest refraction, and the adjustment/lock-in procedure may make vision worse, such that it may be necessary to remove and replace the LAL. Vision loss may be permanent and may not be improved by replacing the LAL. There is a potential risk for UV-induced damage to the eye, including the cornea and retina, which may be permanent. UV light can sometimes cause a reactivation of previous herpes virus infection in the eye. A reactivation of herpes virus can cause scarring of the cornea, blurred vision, eye pain, extreme light sensitivity, permanent loss of vision, and possible need for corneal transplant. Temporary or persistent erythropsia and/or temporary or persistent color vision deficiency may occur. Corneal dryness and corneal abrasions from the lens used for adjustment and lock-in can occur. After the lens adjustment(s) or after the lens lock-in procedures, discomfort, itching and light sensitivity may occur. In cases where a spherocylinder adjustment is performed, it

is possible that visual disturbances may occur if the IOL rotates or if the correction is not performed on the correct axis of astigmatism.

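### For former CSP-037-MX eyes, the synopsis excludes a history of ocular herpes simplex, Section 6.2 omits that exclusion, and nothing says which list prevails

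*Combined protocol and SAP*

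**What the plan says.** The synopsis ends its exclusion list for former CSP-037-MX participants with "Former CSP-037-MX study eye with history of ocular herpes simplex virus". In Section 6.2 the list under the same heading ends one item earlier, with "Subjects who the doctor believes will be unable to maintain steady fixation that is necessary for centration of the LDD light treatment", and Section 7 follows directly.

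Section 6.2 does contain a herpes item, "Study eye with history of ocular herpes simplex virus", but in the list for subjects who were not in CSP-037-MX.

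One sentence decides which list governs the former eye: "The former CSP-037-MX study eye must meet all inclusion/exclusion criteria as specified below for subjects who previously participated in CSP-037-MX". It stands in the synopsis (Study Design), in Section 4 and in Section 7.2. Each time, the next sentence sends the fellow eye to the new-subject list. The general rule, in the synopsis and in Section 6, is that "eyes must meet all applicable inclusion criteria and none of the exclusion criteria as described".

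On risk, Section 10.6 says that "UV light can sometimes cause a reactivation of previous herpes virus infection in the eye", and names corneal scarring, permanent loss of vision and possible corneal transplant among the consequences.

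**The concern.** Two current lists answer the same eligibility question differently. A site that screens from the synopsis excludes a former eye with a herpes history; a site that screens from Section 6.2 has no listed reason to. The protocol ties this criterion to a serious harm from the study treatment. Former eyes enter without earlier LDD treatment (Section 6), so the UV treatments given under this protocol are their first from the LDD.

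At stake are whether such an eye may be treated and whether its enrolment counts as a deviation under Section 12.7. The analysis populations in Section 8.1 are not affected.

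**Working it through.** No formula applies and the plan gives no figure to reproduce. The check is an item-by-item comparison of the synopsis with Sections 6.1 and 6.2, followed by a search for any text that settles the difference.

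**1. Count of items**

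| List | Synopsis | Section 6 | Difference |
|---|---|---|---|
| Inclusion, new subjects | 10 | 10 | Grammar only, in the age item |
| Inclusion, former subjects | 3 | 4 | Section 6.1 adds the word *currently* to the item on acuity potential in the non-study eye (content); it also lists consent (layout only) |
| Exclusion, new subjects | 18 | 18 | Corneal dystrophy: study eye in the synopsis, either eye in Section 6.2 (content) |
| Exclusion, former subjects | 4 | 3 | Herpes history missing from Section 6.2 (content) |

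The consent item is layout only because the synopsis, Section 4 and Section 7.2 already require that consent in running text. Differences in content: 1 + 1 + 1 = 3. Of these, one (herpes) has a UV risk stated in Section 10.6.

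**2. Where the governing sentence leads.** It refers to criteria specified below. Read in the synopsis, that is the four-item list. Read in Section 4, it is the three-item list in Section 6.2. Read in Section 7.2, which governs subject entry, no list follows.

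**3. Whether the new-subject herpes item fills the gap.** It does not. The former eye is assigned to the former-participant list and only the fellow eye to the new-subject list. Within Section 6.2, the herpes exclusion therefore covers a former subject's fellow eye but not the eye already implanted.

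**4. Whether the general rule fills the gap.** It can be read as requiring that an eye clear both lists. But it names no list, and in Section 6 it introduces the lists that lack the item.

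**5. Whether another provision fills the gap.** Section 7.3.2.1 provides for delaying light treatment when an ocular adverse event or other safety concern exists. That concerns postponement, not eligibility. It does not mention herpes history, and Section 10.4.1 says pre-existing conditions are not adverse events.

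**6. When the history is taken.** In Section 7.4 the preoperative visit does not apply to a former subject with only the former eye enrolled; the Table 1 footnote reads "Visits only required for subjects who did not previously participate in" the earlier study. Table 1 schedules ocular history for former subjects at Postop Week 3, which Section 7.4 defines as "Days 17 to 30 days postop: Adjustment #1". The history is thus due at the visit of the first adjustment, and a site using Section 6.2 has no herpes criterion to apply to it.

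**7. What happens to an affected eye.** Section 7.7.2 provides for withdrawal for failed criteria before implantation. Section 7.7.4 limits discontinuation after implantation to explantation or death. Former eyes are already implanted, so neither section clearly covers one found ineligible.

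**The case against.** The strongest reply is that the lists differ by omission and do not conflict. Nothing in Section 6.2 expressly admits a former eye with a herpes history, and an eye that clears four items also clears three. The synopsis is numbered Section 1 of the protocol and contains both the general rule and the governing sentence, each leading to the list with the herpes item. On that reading, enrolling such an eye breaches Section 1. This is a fair reading, but the protocol does not state it, and a reader who follows Section 4 into Section 6 reaches the shorter list with no sign that it is incomplete.

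A second reply is that the bullet may have been lost when the text was extracted, since parts of Table 1 appear to be missing without a mark. That cannot be excluded outright, but nothing points to it here: the list ends on a complete bullet, immediately before Section 7.

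Third, the Week 3 ocular history could work as a safeguard, because nothing says it is taken after the adjustment. That is correct, but taking a history protects the eye only if a criterion says what to do with the answer.

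Fourth, the CSP-037-MX entry criteria are not in the documents, so these eyes may already have been screened for herpes. This stands as a limit on what can be said about frequency; it does not reconcile the lists.

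Finally, the other differences are minor. That is accepted: no different enrolment decision has been shown to follow from the added word *currently*, and the dystrophy item rests on investigator opinion. They are included only because one amendment can settle them all.

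**Conclusion.** The inconsistency is real and must be fixed. The former-participant exclusions number four in the synopsis and three in Section 6.2; the missing one is a history of ocular herpes simplex, and no passage sets an order of precedence. The importance rests on the protocol's own statement of UV reactivation risk.

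Confidence in the textual finding is high, on the assumption that the Section 6.2 list is complete as it appears. The number of eyes affected is unknown and may be zero, because neither the number of former eyes nor the CSP-037-MX entry criteria are given. No endpoint, population or analysis changes. The corneal dystrophy and *currently* differences are secondary and carry no stated UV risk. This review takes no position on which eligibility rule is right.

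**What to change.** In one amendment:

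- Reconcile the synopsis lists with Sections 6.1 and 6.2 item by item until they are identical. At a minimum, settle herpes history in former CSP-037-MX eyes, corneal dystrophy (study eye or either eye) and the word *currently*, and align the consent item.
- In Section 7.2, replace the reference to criteria below with a citation of Sections 6.1 and 6.2 by number, and make those sections the single source for screening.
- State how any affected eye already enrolled is to be handled, since Sections 7.7.2 and 7.7.4 do not clearly cover it.

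The sponsor decides which wording stands. The cost is four list items, one cross-reference, a statement on affected eyes and any screening form that repeats the criteria. No analysis has to be changed. Whether any eye's eligibility changes cannot be told from the documents.
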